By assessing immunity across different demographics (age and geographical area), this study aims to highlight specific populations at risk of measles outbreaks. This information will enable targeted public health interventions, such as tailored vaccination campaigns in areas or age groups with lower seroprevalence, ultimately improving overall vaccination coverage and preventing future outbreaks. Additionally, it will enable us to estimate the population's overall susceptibility to measles and monitor progress toward measles elimination goals (21).

In addition to assessing seroprevalence for measles, this study will also explore the seroprevalence of other biomarkers of infectious diseases that are of public health concern in Belgium. These may include diseases such as mumps, rubella, diphtheria, tetanus, pertussis and hepatitis, amongst others. A preliminary list of potentially included pathogens, along with the rationale for their inclusion, is provided in Appendix 1. This list is intended to support further discussions; final decisions on which pathogens will be included will be made in consultation with the steering committee. These data aid in identifying at-risk populations, guiding public health interventions, and providing a more accurate measure of disease burden, including underreported infections.

Proposed methods

Objectives

- 1. Establish a national serum bank to estimate the age-specific prevalence rates of biomarkers for infectious diseases in Belgium:
 - a. Estimate the measles seroprevalence in the Belgian population
 - across different age groups and geographical areas to identify potential gaps in immunity,
 - ii. identify risk factors for susceptibility (age, region),
 - iii. assess the relationship between immunity estimates and vaccination coverage,
 - iv. compare the findings with results from previous studies to interpret trends over time.
 - b. Estimate the seroprevalence of other pathogen-specific biomarkers in the Belgian population, based on the priority list determined by the steering committee, to guide public health interventions.

Study population

The target population of this study is the entire Belgian population. The study population consists of individuals living in Belgium, of all ages, who have had a blood sample analyzed at one of the laboratories participating to the sample collection during the sample collection time period.

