Participating laboratories will fill in a password-protected Excel document containing an overview of the pre-filled sample codes (Appendix 2). In the first tab of the document, the laboratory fills for every included sample date of birth, gender and postal code of the patient whose blood/serum sample was labelled with the corresponding sample code. Using this information, the built-in validation rules of the spreadsheet will flag potential duplicates and ask the lab collaborator to verify and exclude samples from the same patient. The date of birth and postal code variables will then be automatically converted into age and arrondissement on a second tab of the Excel-sheet. Only the second tab, containing sample code, age (in years), gender and arrondissement, will be transferred to Sciensano. This procedure allows to avoid multiple samples from the same patient being included (since the sample collection will run over several months) whilst at the same time ensuring only anonymous data are shared with Sciensano. Laboratories will be asked to destroy the original Excel files after the collection period has ended.

A verification will be performed by an epidemiologist of Sciensano to ensure that information on age and gender collected through the Excel document matches the sample labels.

The final serum bank and the data files will be the responsibility of Sciensano.

Laboratories will be invited to an online meeting beforehand, outlining the study methodology and sampling procedure. A recording of the meeting as well as additional written documentation will be available afterwards. A project web-page on the Sciensano website will be developed to enable participating laboratories to access useful information as well as contact details in case of further questions.

Collection of data at laboratory in charge of testing

Laboratory testing results will be communicated to the study team through an Excel file only containing unique sample codes and test results, to ensure a maximum protection of data. The file will be stored at Sciensano on a secured and confidential file server. Since the data are anonymized, it will not be possible to link serological results to specific individuals, and therefore, no individual feedback will be provided.

Data analysis

General

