For each pathogen studied, we will calculate crude prevalence of seronegative, equivocal (if applicable) and seropositive results for Belgium. Since all collected samples will be tested for a certain pathogen by a single laboratory, we avoid any potential inter-laboratory variability in testing methodology. We assume that differences observed between laboratories reflect geographical variation rather than laboratory artifacts. However, since laboratories serve patients residing outside their province, the actual geographical distribution of samples may deviate from the intended stratification. To address this discrepancy, post-stratification weights will be applied to adjust for the spatial disparity between the data and the Belgian population. Moreover, seroprevalences will be adjusted for test sensitivity and specificity for the pathogen under investigation.

Statistical analysis will be done with R. Dummy tables are presented in Appendix 3. The specific analysis performed for each of the pathogens will be stored in an R file, containing explanation of the analysis. For each pathogen, these files will be stores in a secured folder at Sciensano.

Measles

For measles, measles vaccine target groups will additionally be defined as those targeted by measles vaccination (at least 1 year old and born in or after 1985) versus those not targeted (born before 1985, or not yet 1 year old at time of sampling). Within the measles vaccine-targeted group, two subgroups will be defined, with the 2-10 year olds as the ones targeted by minimal 1 dose and the 11-40 year olds as the ones targeted by 2 doses. The association between seronegativity and age group, sex, and province will be estimated using log binomial regression per measles vaccine target group. Adjusted prevalence ratios (aPR) and 95% confidence intervals (CI) will be calculated. P-values <0.05 will be considered significant.

The geometric mean titers (GMTs) for anti-measles IgG will be calculated and adjusted for clustered sampling and standardized for age, sex and population per province according to the Belgian population structure in 2025. The 95% confidence intervals (95%CI) will be estimated. Differences in GMTs between sex, region and age group will be assessed with the adjusted Wald chi-square test.

Quality assurance

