Tetanus	anti-TTIgG	 All ages, incl. 65+ 	Classic marker of vaccination coverageUnclear population immunity in elderly	
Diphtheria	Anti-DT	•	 2022-2023 outbreak in Belgium including 1 fatal case (16y) Emergence of macrolide-resistant C. Diphtheria C. Ulcerans infections in elderly 	Risk groups Belgium 2014- 2016 Belgium, 2012
CMV	anti-CMV IgG	all ageswomen reproducti ve age	 Ph3 clinical trials vaccine underway cCMV big public health impact 	Belgium 2002,2006

Appendix 2

Data collection sheet for laboratories (only seen by laboratories)

Laboratory	Nb	1
------------	----	---

Unique code	Sample date	Date of birth	Gender	Postcode
Laboratory/gender/age				
Data collection sheet delivered i	from laboratories to Scier	nsano		
Laboratory Nb 1				
Unique code	Sample A date	\ge Ge	nder Arro	ondissement
Laboratory/gender/age				

Appendix 3

Dummy tables

1. Study population characteristics

Variable	Category	N (%) – Study population	N (%) – Belgian population
Age	1-4 yo		
	5-9 yo		
	10-14 yo		
	15-19 yo		
	20-29 yo		
	30-39 yo		
	40-49 yo		
	50-59 yo		
	60-69 yo		
	≥ 70 yo		
Sex	Female		
	Male		
Provinces	Antwerp		
	West Flanders		
	East Flanders		
	Limburg		
	Flemish Brabant		
	Walloon Brabant		
	Hainaut		
	Namur		
	Liege		
	Luxembourg		
	Brussels		

2. Seroprevalence by Demographic Characteristics – one table per pathogen

Characteristic	n tested	n seropositive	% Seropositive (95% CI)
Age group (years)			
Sex			
Region/provinces			

3.	Comparison of Seroprevalence over time (with previous seroprevalence study) – one table
	per pathogen

Birth cohort	Time point	n tested	n seropositive	% Seropositive (95% CI)
Targeted by measles vaccination	Study 2013/2015			
	Study 2025/2026			
Not targeted by measles vaccination	Study 2013/2015			
	Study 2025/2026			

4. Log binomial regression analysis (Prevalence Ratios) – one per pathogen

Variable	Adjusted Prevalence Ratios (95% CI)	p-value
Age		
Sex		
Region/provinces		

Appendix 4

Scientific steering committee – Composition

Function/entity	Expertise	Number of representatives
FOD Volksgezondheid (federal authorities)	Public Health	1
DepZorg (regional authorities)	Public Health	1
AViQ (regional authorities)	Public Health	1
Vivalis (regional authorities)	Public Health	1
ONE (regional entity)	Public Health (vaccination)	1
University of Hasselt – University of Antwerpen	Biostatistics	2
University of Gent (UGent) – University Hospital of Gent (UZ Gent)	Infectious diseases (adults)	1

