1.3. Age-based sampling structures

To compare the impact of different sampling strategies on the precision of seroprevalence estimates, we considered three age-based sampling structures, as described in Blaizot et al. (2019) [1]. First, a population-based structure, proportional to the demographic distribution from the 2021 national census (Figure S2). Second, a survey-based structure, reflecting the age distribution observed in the 2013 Belgian serological survey, in which children and adolescents were oversampled (Figure S3). Third, a uniform structure, assuming equal sampling across all ages. These three structures were used to simulate synthetic datasets under varying total sample sizes, allowing comparison of the resulting precision across strategies.

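### The 'Targeted' row of dummy table 3 is labelled a birth cohort but sets births 1985-2012 against births 1985-2024, which dilutes the within-cohort decline in measles immunity

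*Protocol*

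**What the plan says.** Objective 1.a.iv is to "compare the findings with results from previous studies to interpret trends over time". The only table laid out for this is dummy table 3 in Appendix 3, whose title begins "Comparison of Seroprevalence over time (with previous seroprevalence study". Its first column is headed 'Birth cohort'. The two entries are the group targeted by measles vaccination and the group not targeted, each with one line for 2013/2015 and one for 2025/2026, giving number tested, number seropositive and per cent seropositive with a 95% CI.

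The Measles part of the Data analysis section defines the targeted group as "at least 1 year old and born in or after 1985". The other group is everyone born before 1985 or under one year old at sampling.

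For seroprevalence, the General part of Data analysis plans post-stratification weights for spatial disparity and an adjustment for test sensitivity and specificity. Standardisation for age, sex and province is stated for geometric mean titres only. Appendix 5, section 1.3, describes the 2013 survey as one "in which children and adolescents were oversampled".

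On data transfer, the Data collection procedure says: "Only the second tab, containing sample code, age (in years), gender and arrondissement, will be transferred to Sciensano". It adds: "Laboratories will be asked to destroy the original Excel files after the collection period has ended". The Data transfer and Vulnerable populations sections list the same items. The sheet delivered to Sciensano in Appendix 2 also has a sample date column.

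**The concern.** A reader of a table headed 'Birth cohort', with two survey dates, will take each row as the same people followed over twelve years. The targeted row is not that. The start of its birth range is fixed at 1985 but the end moves with the survey, so twelve recently vaccinated birth years enter in 2025 and raise the later figure. No stated weighting makes the age or cohort mix of the two surveys comparable.

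This matters because possible waning in adults is one of the reasons Appendix 1 gives for testing measles, and because the study is meant to inform catch-up vaccination. The cohorts that would be considered for catch-up are those whose decline the row dilutes.

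**Working it through.** **1. The definition against the plan's own age limit.** 2025 - 1985 = 40, which matches the protocol's upper age of 40 for the targeted group. The same rule in 2013 gives 2013 - 1985 = 28. The row therefore covers ages 1-28 (28 birth years) in 2013 and ages 1-40 (40 birth years) in 2025. The 12 extra birth years are 2013-2024.

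**2. Weight of the new cohorts.** From Table 1 in the Sample size section, the bands from 1 to 40 years sum to 450 + 450 + 300 + 450 + 450 + 750 = 2,850 (with 1,050 in the 40-65 band, 3,900 in total). Spreading samples evenly within bands, ages 1-12 take 450 + 450 + 300 x 3/5 = 1,080, and 1,080/2,850 = 38%.

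**3. Illustrative effect.** Inputs from Appendix 5, section 1.2.2: seroconversion 0.96, waning 0.008 per year after dose 1 and 0.009 after dose 2. First-dose coverage is 96% (Appendix 5, Table 1). Assumption: the second dose restores the starting level at age 12. The starting level is 0.96 x 0.96 = 0.9216.

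- Ages 1-12: p(a) = 0.9216 exp(-0.008(a - 1))
- Ages 13 and over: p(a) = 0.9216 exp(-0.009(a - 12))

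Means over single years of age:

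- Births 1985-2012 in 2013 (ages 1-28): 86.6%
- The same births in 2025 (ages 13-40): 81.1%, a change of -5.5 points
- New entrants in 2025 (ages 1-12): 88.2%
- Table row in 2025, even ages: (28 x 81.1 + 12 x 88.2)/40 = 83.2%, a change of -3.4 points
- Table row in 2025, Table 1 quotas: 83.9%, a change of -2.7 points

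**4. Sensitivity to the 2013 age mix.** That mix is in a figure not shown, so oversampling of ages 1-19 is an assumption. Same-cohort figures use the 2013 weights at both dates; gaps come from unrounded values.

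| 2013 mix | 2025 mix | Same cohorts | Table row | Gap |
|---|---|---|---|---|
| Even | Even | -5.5 | -3.4 | 2.1 |
| Even | Quotas | -5.5 | -2.7 | 2.9 |
| Ages 1-19 doubled | Quotas | -5.0 | -3.4 | 1.5 |
| Ages 1-19 tripled | Quotas | -4.7 | -3.7 | 1.0 |

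**5. Sensitivity to the second-dose formula.** The formula is garbled in the text available. If its second line applies second-dose coverage alone (83%), the same cohorts fall 9.7 to 10.4 points, against 2.7 to 5.0 in the row with Table 1 quotas (4.1 to 6.3 with even ages in 2025). If births 1985-2000 instead start from an assumed 80-90% in 2013 and wane for 12 years, the factor is exp(-0.009 x 12) = 0.898. That group then falls 8.2 to 9.2 points while the row falls 1.1 to 4.0. The row shows the smaller decline in every run.

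**6. Birth year from the transferred data.** Age in completed years plus sample date fixes birth year to two adjacent calendar years. At the 1985 cut the ambiguous ages are 40 in 2025 and 41 in 2026. If sample date is not transferred and the cut is made on age alone, with sampling even from mid-2025 to mid-2026, about 12.5% of 40-year-olds and 12.5% of 41-year-olds fall on the wrong side. With 1,050/26, or about 40 samples per year of age, that is about 5 each way: about 10 of 3,900, or 0.3%.

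**The case against.** Several points on the other side are sound.

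- **Programme-level meaning.** Immunity among everyone the programme targets at each date is a legitimate quantity. That supports keeping the row, but not calling it a birth cohort.
- **Not wholly crude.** A reader might infer raw percentages from the n/n/% layout. The plan does state spatial weights and a test-performance adjustment. What is missing is age or cohort standardisation.
- **Other outputs show age.** The targeted group is split into 2-10 and 11-40 years, and dummy table 2 gives seroprevalence by age group. Neither is laid out as a comparison with 2013.
- **Re-testing of 2013 sera.** This deals with assay comparability, not with cohort or age mix.
- **Half the table.** The non-targeted row gains no new birth cohorts, since it ends at 1984 in both surveys and under-ones have no quota in Table 1.
- **Detail for a later plan.** Standardisation could be settled in a statistical analysis plan. The row definition and its label, however, are already fixed here and conflict.

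A reader might also infer that the transfer loses the birth year needed to match cohorts. The documents do not support that: the Appendix 2 sheet has a sample date, which with age is adequate for banded cohorts apart from edge years. Nor do they support a larger decline obtained by waning every cohort for 12 years at about 0.0085 (86.6% to 78.2%, or -8.4 points). That carries children aged 1-11 in 2013 straight past their second dose.

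**Conclusion.** The point holds for the targeted row. As defined, it compares different sets of birth years under a heading that promises the same ones, and no stated adjustment corrects this. The within-cohort decline is attenuated by about 1 to 3 points in the runs with a reset at age 12. The gap is wider under the literal second-dose reading.

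It would go too far to say that the table conceals waning: a decline still appears in every run. The sizes are illustrative. They rest on 96% coverage in all cohorts, on even spread within age bands, on an assumed 2013 age mix and on one reading of the second-dose formula. Appendix 5 itself starts births 1984-2000 from observed 2013 serology, which is not tabulated.

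The data-transfer issue is secondary. It is an inconsistency over sample date with a very small effect at the 1985 cut.

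**What to change.** - In dummy table 3, compare fixed birth-year bands present in both surveys, for example 1985-1999, 2000-2012, and before 1985 restricted to birth years sampled both times. Standardise both surveys to one common birth-year, sex and province distribution, and use the re-tested 2013 results.
- Show births after 2012 in a separate row, for 2025/2026 only.
- Keep the all-targeted row if wanted, labelled as a programme-level figure and not as a birth cohort.
- Reconcile the Data transfer, Data collection procedure and Vulnerable populations sections with Appendix 2: either confirm that sample date is transferred, or add a year-of-birth column derived by formula on the second tab. Do this before the laboratories destroy their files.

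The cost is one changed table and, if year of birth is added, one extra spreadsheet column to mention to the ethics committee. The number of samples does not change.

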1.1. Data

1.1.1. Serological data

Serological testing for the presence of measles antibodies was conducted on large representative national serum banks in Belgium [4]. Serum samples were collected in 2013, from residual blood samples used for routine laboratory testing.

[figure not shown]

Figure 1. Seroprevalence of measles by birth year in Belgium (2013). The black points represent the empirical seroprevalence estimates for each birth year, while the red vertical bars indicate the 95% Clopper-Pearson confidence intervals.

1.1.2. Vaccination coverage

Vaccination coverage estimates for Belgium for both recommended measles-mumps-rubella (MMR) vaccine doses were taken from [5], [6], [7], [8], [9], [10], [11], [12], [13]. Detailed coverage information can be found in Hens et al. (2016) [2]. Most recent vaccination coverage estimates are updated annually by Sciensano using population-weighted estimates, but new survey data are not collected every year (Table 1, [14]). For years without reported coverages between 2001 and 2025, we applied a linear interpolation approach based on the available data in order to generate a continuous perspective on annual coverage estimates for MMR1 and MMR2 (Figure S1). When regional data were missing, national estimates were used as a proxy.

Year	Region	MMR1	MMR2
2019	Wallonia	96,50%	
2019	Brussel	94,80%	
2019	National	96%	82%
2020	Flanders	96,10%	89,20%
2020	National	96%	83%
2021	Wallonia		73,00%
2021	National	96%	83%
2022	National	96%	83%
2023	National	96%	82%

Table 1. Vaccination coverage estimates for the period 2019-2023 [14].

1.2. Cohort model to project seroprevalence to 2025

The model builds on the multicohort framework introduced by Abrams et al. (2014) in the context of mumps and further exemplified for measles by Hens et al. (2015) [2], [3], which uses historical serological data and vaccination coverage information to estimate age-specific immunity profiles in later years. In our case, we adapted the aforementioned approach to project measles seroprevalence from the 2013 national survey to 2025. This was done in two steps: (i) modelling the age-specific seroprevalence data from 2013 using a generalised additive model (GAM), and (ii) projecting the immunity profile to 2025 using a dynamic cohort model that accounts for birth year, vaccination coverage (MMR1 and MMR2), and waning immunity over time.

1.2.1. A model for the serological data in 2013

We used a GAM for binary outcome data (with binary response variable indicated seropositivity status) to estimate age-specific measles seroprevalence in Belgium based on the 2013 serological survey data. A complementary log-log link function was used to link the seroprevalence to age. The model included a smooth function of age to capture a potential non-linear trend in humoral immunity. Therefore, the GAM [15] can be formulated as follows:

$$Y|a \sim B(\pi(a))$$

cloglog($\pi(a)$) = f(a),

where f(.) represents a smooth function for age which is constructed based on cubic spline basis functions.

The resulting age-specific seroprevalence profile served as the baseline immunity profile (distribution) (i.e., allowing us to describe the age-specific susceptibility to measles in the population in 2013) for the dynamic cohort model projecting to 2025.

[figure not shown]

Figure 2. Observed seroprevalence and smoothed estimates by region in 2013. Age-specific seroprevalence (red dots with binomial confidence intervals) and fitted GAM estimates (black line) based on 2013 serological data in Belgium. The generalised additive model was fitted using a complementary log-log link with a smooth term for age.

1.3. Age-based sampling structures

To compare the impact of different sampling strategies on the precision of seroprevalence estimates, we considered three age-based sampling structures, as described in Blaizot et al. (2019) [1]. First, a population-based structure, proportional to the demographic distribution from the 2021 national census (Figure S2). Second, a survey-based structure, reflecting the age distribution observed in the 2013 Belgian serological survey, in which children and adolescents were oversampled (Figure S3). Third, a uniform structure, assuming equal sampling across all ages. These three structures were used to simulate synthetic datasets under varying total sample sizes, allowing comparison of the resulting precision across strategies.

1.4. Simulation framework for sample allocation and precision

To assess the precision obtained under different age-based sampling structures, we simulated synthetic datasets by drawing binomial outcomes from the projected age-specific seroprevalence profile (Section 1.2). For each individual in the simulated sample, seropositivity status was assigned using a Bernoulli distribution with probability equal to the predicted seroprevalence at their age. This process was repeated independently 500 times for each sampling scenario. The resulting datasets were used to estimate the seroprevalence in each of the eight predefined age groups. Following the approach described by Blaizot et al. (2019) [1], precision was defined as half of the width of the 95% simulation-based confidence interval across the 500 replicates (simulation runs), calculated for each age group and overall. This framework enabled direct comparison of the expected estimation precision under each sampling design.

